3.6 Treatment Assignment and Treatment Groups

This is an uncontrolled study in which all subjects receive BRV in doses that are optimally adjusted for each subject. Generally, statistical summaries will present all subjects combined as a single treatment arm unless otherwise indicated.

3.7 Coding dictionaries

Medical history and AEs will be coded using the Medical Dictionary for Regulatory Activities (MedDRA). Medications will be coded using the World Health Organization Drug Reference List (WHO-DRL). Prior and concomitant medical procedures will not be coded.

3.8 Definitions of study-specific derived variables

3.8.1 Calculation of seizure frequency/days

3.8.1.1 Initial seizure data processing

Each seizure code in the clinical database will be reported as 1 of the following codes based on the 1981 International League Against Epilepsy (ILAE) classification: I, IA, IA1, IA2, IA3, IA4, IB, IB1, IB2, IC, II, IIA, IIB, IIC, IID, IIE, IIF, or III. Seizures identified as type III seizures will be reviewed prior to database lock to ensure that such seizures were not misclassified.

With regard to cluster seizures, investigator sites are to report the number of cluster episodes rather than reporting the estimated number of individual seizures. Therefore, no imputation will be applied for the seizure counts corresponding to reports of cluster seizures.

3.8.1.2 Calculation of adjusted seizure frequency

The following derivations apply only to subjects with Partial Onset Seizures.

Baseline POS frequency for seizure types I, IA, IB, IC, and for all seizure types (I+II+III) will be obtained from the Baseline Period of the previous double-blind study.

The total number of seizures for seizure types I, IA, IB, and IC and the total number of seizures for all seizure types (I+II+III) will be calculated overall, by 3-month time intervals, and over the cohort interval for each exposure duration cohort.

All seizure diary during evaluation period will be considered for these calculations.

Twenty-eight day adjusted seizure frequency for seizure types I, IA, IB, and IC, and for all seizure types (I+II+III) will be calculated overall, within each 3-month time interval, and over each exposure duration cohort interval by dividing the total number of seizures for each seizure type by the number of days for which the diary was completed overall, within each 3-month interval, and within each exposure duration cohort interval, and multiplying the resulting value by 28.

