3.2 Analysis time points

3.2.1 First and last dose of BRV

Unless otherwise noted, all references to the first dose of BRV in this SAP refer to the first dose of BRV during N01379 (ie, not the first dose of BRV from the previous study in which subjects participated in prior to N01379). Unless otherwise noted, all references to the last known dose of BRV in this SAP refer to the last dose of BRV taken across any study periods (ie, not necessarily the last dose of BRV during the Evaluation Period).

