3.2.4 Study periods

The Baseline Period for N01379 corresponds to the Baseline Period of the previous studies, and is defined for seizure outcomes and direct cost parameters. The Baseline Period is defined as study days on or after the date of Visit 1 and prior to the date of Visit 2 for N01258 and study days on or after the date of Visit 1 and prior to the date of Visit 3 for N01358.

The study is divided into 3 periods: Evaluation Period, Down-Titration Period, and Post-Treatment Period. A subject is classified as “discontinued” if the subject has a termination case report form (CRF) or has an early discontinuation visit (EDV). A subject is classified as “completed” if this subject completes the full extent of the study as defined in the protocol at database lock.

A “discontinued” subject can be potentially slotted into the 3 periods of the study. The following algorithms will be used to slot the subject appropriately into the Evaluation Period, Down-Titration Period, and Post-Treatment Period.

- For Evaluation Period, the start date is the date of first dose of BRV, and the following algorithm is used to determine the end date:
 - If the subject enters the Down-Titration Period, then the date of EDV is the end date;
 - If the subject does not enter the Down-Titration Period but meets 1 of the following criteria, the Evaluation Period ends on date of last dose of BRV:
 - Without an EDV but having a termination CRF,
 - With an EDV and having a termination CRF,
 - With an EDV and the date of EDV prior to the database lock date and having no termination CRF.

- A subject is considered entering Down-Titration Period only if the subject has an EDV and at least 1 dose of study drug after the date of EDV, the start date of Down-Titration Period is set as 1 day after the date of EDV, and the Down-Titration Period ends on date of last dose of BRV. A subject without an EDV but having a termination CRF or with an EDV but without any dosing of study drug after the EDV will not have the Down-Titration Period, and no artificial Down-Titration Period will be created for analysis.
- A subject is considered entering the Post-Treatment Period if the subject has at least 1 contact (scheduled visit, unscheduled visit, or telephone contact) after the date of last dose of BRV. The Post-Treatment Period starts 1 day after date of last dose of BRV irrespective of entering the Down-Titration Period, and there is no end date.

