3.2.7 Exposure duration and exposure duration cohorts

At the final analysis, the overall duration of exposure (or On Treatment Period) will be calculated as the date of last dose of BRV minus the date of first dose of BRV plus 1 day.

Each subject will be classified into one or more of the following exposure duration cohorts based on the duration of BRV exposure as calculated above:

All subjects	≥1 day
≥3 months	≥90 days
≥6 months	≥180 days
≥12 months	≥360 days

This categorization will continue in 6-month increments past 12 months up to a time point that will be determined based on cumulative exposure at the time of the database lock.

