3.8.1.3 Calculation of adjusted seizure days

The following derivations apply only to subjects with Primary Generalized Seizures, based on the 1981 ILAE classification, Primary Generalized Seizures include the generalized seizure types and unclassified seizure types.

Baseline seizure days for seizure types II, IIA through IIF, and for all seizure types (I+II+III) will be obtained from the Baseline Period of the previous study.

The total number of seizure days for seizure types II, IIA through IIF, and the total number of seizure days for all seizure types (I+II+III) will be calculated overall, by 3 month time intervals, and over the cohort interval for each exposure duration cohort. The same seizure diary data defined in the Section 3.8.1.2 for POS frequency will be considered.

Twenty-eight day adjusted seizure days for seizure types II, IIA through IIF, and for all seizure types (I+II+III) will be calculated overall, within each 3-month time interval, and over each exposure duration cohort interval by dividing the total number of seizure days for each seizure type by the number of days for which the diary was completed overall (ie, over the periods defined in the Section 3.8.1.2), within each 3-month interval, and within each exposure duration cohort interval, and multiplying the resulting value by 28.

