8.1.1 Partial onset seizure frequency

Twenty-eight day adjusted POS frequency will be summarized with quantitative descriptive statistics for all subjects for the Baseline Period, the On Treatment Period, and by 3-month time intervals over the On Treatment Period. The summary over the On Treatment Period will include all subjects in the POS Efficacy Analysis Set. Similar summaries will be provided for the full cohort interval and by 3-month time intervals for each exposure duration cohort.

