8.1.2 Percent reduction in POS frequency

Percent reduction in POS frequency from Baseline to the On Treatment Period will be calculated as follows, where On Treatment Period Frequency is the 28-day adjusted POS frequency during On Treatment Period and Baseline Period Frequency is the 28-day adjusted POS frequency during the Baseline Period of the previous study.

$$\% \text{ Reduction} = 100 \times \frac{\text{Baseline Period Frequency} - \text{On Treatment Period Frequency}}{\text{Baseline Period Frequency}}$$

A similar calculation applies to each 3-month time interval over the On Treatment Period and for the cohort interval for each exposure duration cohort.

Percent reduction from Baseline for POS frequency will be summarized with quantitative descriptive statistics for the On Treatment Period, and by 3-month time intervals over the On Treatment Period. The summary over the On Treatment Period will include all subjects in the POS Efficacy Analysis Set. Similar summaries will be provided for the full cohort interval

and by 3-month time intervals for each exposure duration cohort. Percent reduction from Baseline for POS frequency will be summarized in the same manner by geographic region.

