8.1.3 Responder outcome for POS frequency

Responders over the On Treatment Period are defined as subjects with a 50% or greater reduction in 28-day adjusted POS frequency from Baseline to the On Treatment Period. A similar calculation applies to each 3-month time interval over the On Treatment Period and for the cohort interval for each exposure duration cohort.

The number and percentage of responders for POS frequency will be summarized for the On Treatment Period, and by 3-month time intervals over the On Treatment Period. The summary over the On Treatment Period will include all subjects in the POS Efficacy Analysis Set. Similar summaries will be provided over the full cohort interval and by 3-month time intervals for each exposure duration cohort. Responder rates for POS frequency will be summarized in the same manner by geographic region.

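### SAP 8.1.1 to 8.1.3 compute the seizure outcomes over the On Treatment Period, taper days included, although SAP 3.8.1.2 and the variable definitions limit them to the Evaluation Period

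*SAP*

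**What the plan says.** **Evaluation Period.** The derivation of adjusted POS frequency (SAP 3.8.1.2) fixes the diary data: "All seizure diary during evaluation period will be considered for these calculations". For seizure days in PGS subjects, SAP 3.8.1.3 adds: "The same seizure diary data defined in the Section 3.8.1.2 for POS frequency will be considered". Protocol 4.2.1 and 4.2.2 and SAP 2.2.2.1 and 2.2.2.2 define the seizure variables over the Evaluation Period too. For a discontinuing subject, SAP 3.2.4 sets its end: "If the subject enters the Down-Titration Period, then the date of EDV is the end date".

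**On Treatment Period.** SAP 8.1.1 summarises POS frequency "for the Baseline Period, the On Treatment Period, and by 3-month time intervals over the On Treatment Period". SAP 8.1.2 says "Percent reduction in POS frequency from Baseline to the On Treatment Period will be calculated as follows", and its formula uses the same term. SAP 8.1.3 reads: "Responders over the On Treatment Period are defined as subjects with a 50% or greater reduction in 28-day adjusted POS frequency". The term is defined in SAP 3.2.7, where "the overall duration of exposure (or On Treatment Period) will be calculated as the date of last dose of BRV" minus the first-dose date plus 1 day. Under SAP 3.2.1, mentions of the last known dose "refer to the last dose of BRV taken across any study periods".

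**Looser wording.** SAP 4.2 bases the rates of early discontinuers on diary kept while BRV was being received. SAP 8.2.1.1 assesses seizure freedom over the time on BRV, where SAP 2.2.2.2 names the Evaluation Period. SAP 3.2.5 admits a subject to a 3-month efficacy interval by an end date that it does not define.

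**The concern.** For a subject who tapers, the On Treatment Period is the Evaluation Period plus the Down-Titration Period. Diary data from the taper should exist, because Protocol 8.6 has a new diary card dispensed at the Early Discontinuation Visit (EDV) to subjects who will down-titrate. Two programmers could therefore each follow the SAP and obtain different values of the same variable.

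All three secondary efficacy variables are involved, and they carry the maintenance-of-efficacy objective. Taper days are reduced-dose days during withdrawal and lie outside the protocol's variable. They weigh most in early discontinuers, the group whose influence SAP 4.2 says it wants to separate out.

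**Working it through.** The documents give no sample size, power or effect figure to reproduce. The check compares the two windows and then does day-count arithmetic.

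**Step 1: the windows.** Day 1 is the first dose.

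| Subject | Evaluation Period ends (SAP 3.2.4) | On Treatment Period ends (SAP 3.2.7, 3.2.1) | Difference |
|---|---|---|---|
| Discontinues and tapers | EDV | Last dose, at end of taper | Length of taper |
| Discontinues, no taper | Last dose | Last dose | None |
| Completes and tapers | Not stated; Protocol 5.1.1 gives the Last Evaluation Period Visit | Last dose, at end of taper | Length of taper |

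**Step 2: length of taper.** Protocol 5.1.1 allows up to 4 weeks, with weekly steps of at most 50 mg/day and a last week at 20 mg/day. At maximum steps, a taper from 200 mg/day is 150, 100, 50, 20, or 28 days. From 150 mg/day it is 100, 50, 20, or 21 days. With a full diary, 28 taper days are 28/118 = 23.7% of On Treatment days after 90 Evaluation days and 28/388 = 7.2% after 360.

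**Step 3: effect on one subject.** These rates are assumptions: 10 seizures per 28 days at Baseline and 5 on BRV. The Evaluation Period reduction is then exactly 50.0%, a responder. Let E be Evaluation days, with a 28-day taper of which the last L days are at the Baseline rate.

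On Treatment frequency = [5 × (E + 28 − L) + 10 × L] / (E + 28)

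| Assumption | E = 90 | E = 360 |
|---|---|---|
| Effect lost for the whole taper (L = 28) | 730/118 = 6.19; 38.1% reduction | 2080/388 = 5.36; 46.4% |
| Effect lost in the last week only (L = 7) | 625/118 = 5.30; 47.0% | 1975/388 = 5.09; 49.1% |
| No loss of effect (L = 0) | 5.00; 50.0% | 5.00; 50.0% |

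**Step 4: who changes responder status.** If R is the Evaluation Period reduction, the On Treatment reduction is R × (E + 28 − L)/(E + 28). Status changes when R is at least 50% but below 0.5 × (E + 28)/(E + 28 − L):

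- L = 28: below 59/90 = 65.6% at E = 90, and below 194/360 = 53.9% at E = 360.
- L = 7: below 59/111 = 53.2% at E = 90, and below 194/381 = 50.9% at E = 360.

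**Step 5: linked rules.** With an EDV on Day 62 and a 28-day taper, the last dose is on Day 90. The subject enters the Months 1-3 efficacy interval if the end date in SAP 3.2.5 is the last dose, but not if it is the end of the Evaluation Period. For seizure freedom, 152 seizure-free Evaluation days plus 28 seizure-free taper days make 180. That can count as 6-month freedom under SAP 8.2.1.1 but falls short under SAP 2.2.2.2. Because any continuous interval counts, the longer window can only add seizure-free subjects.

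**The case against.** The strongest reply is that the SAP already settles the data rule and that On Treatment Period is a loose label in Section 8. The opening of Section 8 sends the reader to 3.8.1.2 and 3.8.1.3 for the derivations. SAP 3.5.2 requires a diary day on or before the end of the Evaluation Period, pointing to Section 8, and 8.1.1 says that its On Treatment summary covers the set so defined. SAP 4.2 concerns subjects who discontinue during the Evaluation Period, and without a taper the windows coincide. This stands as the better-supported reading of intent. It does not repair the text: 3.2.7 gives the term an explicit meaning, the 8.1.2 formula uses it, and nothing equates the two periods.

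The second reply is that full return to Baseline for 28 days is a worst case. This also stands. Protocol 2.3 reports efficacy at 50 mg/day, and Protocol 5.4 puts the doses needed at 50 to 100 mg/day. In a taper from 200 mg/day, three of the four weeks are at 50 mg/day or more, so the last-week row in Step 3 is a fair alternative.

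A reader might also infer three stronger points, which the documents do not support:

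- **Exposure cohorts.** Membership in SAP 3.2.7 is explicit, and Protocol 12.7 asks for results by category of exposure duration. Counting taper days there is not an error, and rebasing the cohorts would be a preference.
- **The 90% diary rule.** One could set BRV-day intervals against Evaluation-only diary and find 152/180 = 84.4%, a failure. No section states that hybrid rule; 8.2.1.1 has its own window and does not cite 3.8.1.2.
- **PGS responders and percent reduction.** All PGS subjects come from N01258. Section 8 excludes N01258 subjects from responder rates and percent reduction because of the 7-day Baseline, so any effect there is largely moot.

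**Conclusion.** The inconsistency is real and should be corrected. As written, SAP 8.1.1 to 8.1.3 depart from the protocol variable for every subject who tapers, and 8.2.1.1 departs from 2.2.2.2 in the same way.

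The consequence is limited. It reaches POS frequency in tapering subjects and, for those from N01358, percent reduction and responder status. Seizure days in PGS subjects and seizure freedom are also touched. Subjects who move to other BRV supply without a taper are unaffected. For a subject exactly at 50%, the reduction moves by 0 to 11.9 percentage points after 90 Evaluation days (50.0 − 38.1) and by 0 to 3.6 after 360 (50.0 − 46.4). These ranges rest on the assumed rates, a full diary and the longest taper.

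A reader might infer that the reported long-term responder rates would be materially wrong. The documents do not support that. They do not give the number of tapering subjects, the taper share shrinks as exposure lengthens, and the pooled effect is probably small. The analyses are descriptive, so no error rate is involved, and the primary objective is safety.

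**What to change.** 1. In SAP 8.1.1 to 8.1.3, replace *On Treatment Period* with *Evaluation Period*. SAP 8.2.2.1 follows by reference.
2. In SAP 4.2 and 8.2.1.1, replace the wording about receiving or being treated with BRV by the Evaluation Period. SAP 8.2.2.4 follows by reference.
3. In SAP 3.2.5, define the end date for efficacy intervals as the end of the Evaluation Period. For completed subjects who taper, use the Last Evaluation Period Visit, as in Protocol 5.1.1, because the algorithm in SAP 3.2.4 covers only discontinued subjects.
4. Leave SAP 3.2.7, including exposure-cohort membership, as it is.

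The cost is SAP wording and matching programming, with no new data. The downside is that up to 28 reduced-dose diary days per tapering subject leave the efficacy summaries.

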3.8.1.3 Calculation of adjusted seizure days

The following derivations apply only to subjects with Primary Generalized Seizures, based on the 1981 ILAE classification, Primary Generalized Seizures include the generalized seizure types and unclassified seizure types.

Baseline seizure days for seizure types II, IIA through IIF, and for all seizure types (I+II+III) will be obtained from the Baseline Period of the previous study.

The total number of seizure days for seizure types II, IIA through IIF, and the total number of seizure days for all seizure types (I+II+III) will be calculated overall, by 3 month time intervals, and over the cohort interval for each exposure duration cohort. The same seizure diary data defined in the Section 3.8.1.2 for POS frequency will be considered.

Twenty-eight day adjusted seizure days for seizure types II, IIA through IIF, and for all seizure types (I+II+III) will be calculated overall, within each 3-month time interval, and over each exposure duration cohort interval by dividing the total number of seizure days for each seizure type by the number of days for which the diary was completed overall (ie, over the periods defined in the Section 3.8.1.2), within each 3-month interval, and within each exposure duration cohort interval, and multiplying the resulting value by 28.

3.8.2 QOLIE-31-P

The QOLIE-31-P is an adaptation of the original QOLIE-31 (Cramer et al, 1998). The QOLIE-31-P includes 30 items grouped into 7 multi-item subscales (seizure worry [5 items], overall quality of life [2 items], emotional well-being [5 items], energy/fatigue [4 items], cognitive functioning [6 items], medication effects [3 items], and social function [5 items]) and a health status item. The QOLIE-31-P total score, subscale scores, and health status item score are calculated according to the scoring algorithm described below, with scores ranging from 0 to 100 and higher scores indicating better functioning. In addition to these 31 items, the QOLIE-31-P includes 7 items assessing the degree of “distress” associated with the topic of each subscale (ie, distress items) and 1 item asking about the relative importance of each subscale topic (ie, prioritization item).

Subscale Scores

As a first step to calculating the subscale scores, the individual responses for the 30 subscale items are rescaled to a 0 to 100 scale with higher scores reflecting better functioning; the rescaled values for each item are defined in Section 13.1. Each subscale score is then calculated by summing the rescaled responses for that subscale and dividing by the number of items without a missing response. A subscale score will be calculated only if at least 50% of the items within the subscale are present.

Total Score

Total score is calculated as a weighted sum of the subscale scores based on the weighting in Section 13.1. Total score will be missing if at least 1 subscale score is missing. Total score will range from 0 to 100 with a higher score reflecting better functioning.

Health Status Item

Responses for the health status item is a multiple of 10 ranging from 0 to 100 with a higher score corresponding to a better health status. The health status item response is analyzed without rescaling.

Distress Items

Each subscale includes 1 distress item. The response for each distress item is an integer ranging from 1 to 5. The response for each distress item will be converted to a 0 to 100 scale (ie, 0, 25, 50, 75, and 100) with a higher score corresponding to greater distress.

Prioritization Item

The response for each subscale for the prioritization item is an integer ranging from 1 to 7. The prioritization ranking is analyzed without rescaling.

3.8.3 HADS

The HADS assessment consists of 14 items that are each scored on a 4-point scale ranging from 0 to 3, with a higher score corresponding to worse anxiety or depression. The depression and anxiety scores will be calculated by summing the scores for the items corresponding to each subscale, as described in the Hospital Anxiety and Depression Scale Manual (Snaith and Zigmond, 1994): the depression score is calculated as the sum of all even-numbered items; the anxiety score is calculated as the sum of all odd-numbered items. Scores for each subscale range from 0 to 21, with higher scores corresponding to a greater level of anxiety or depression.

Missing items will be replaced by the mean of non missing items from the same subscale when calculating the above, provided at least 50% of the items (ie, at least 4 of 7 items) within the subscale are present. A subscale score will not be calculated if more than 50% of the items are missing within a subscale. This rule applies separately to the subscale scores for anxiety and depression; for example, it may be possible to calculate the depression score in cases where the anxiety score is not calculated due to non response.

